12.5.2.1.3 Missing Data Description

Description of missing data patterns will present the number and percentage of patients within each missing data pattern by treatment sequence and overall for the LLMT-6 score and the 6 individual muscle group scores composing the LLMT-6 score (as defined in [Section 10.16](#)).

Description of LLMT-6 score monotone missing pattern will be performed by treatment arm and COVID-19 impact (using indicator variable for COVID-19 impact as defined in [Section 12.5.2.1.2](#)), presenting the number and percentage of patients within each of the following monotone missing data pattern:

- Pattern 1: Patient with no baseline nor post baseline LLMT-6 scores,
- Pattern 2: Patient with a baseline LLMT-6 score but no post baseline LLMT-6 scores,
- Pattern 3: Patient with a baseline LLMT-6 score and LLMT-6 scores up to Day 1H3 only,
- Pattern 4: Patient with a baseline LLMT-6 score and LLMT-6 scores up D21.

This summary will also provide Mean (SD) at Baseline, D1H3 and D21 of each treatment period for each monotone missing data pattern.

12.5.2.1.4 MI Models - General Consideration

Each imputation model will use a common random seed value of 20210714 and any imputed value > 5 will be set to 5 whereas any imputed value below 0 will be set to 0 to account for LLMT score ranging from 0 to 5.

Post Period 1 baseline missing LLMT-6 scores (see [Section 10.16](#)), will be imputed using the strategy described in [Section 12.5.2.1.6](#).

12.5.2.1.5 Monotone data pattern

Prior to performing any imputation methods as described below, intermittent missing scores as well as missing period 2 baseline score will be imputed under a MAR model using a Markov Chain Monte Carlo (MCMC) method to generate monotone missing data patterns within each treatment period.

This will be performed using the MCMC method in conjunction with the IMPUTE = MONOTONE option of the SAS® MI procedure.

First, for patients with no missing Period 1 baseline score but missing Period 2 baseline score, missing Period 2 baseline score will be imputed using a REGRESSION method in conjunction with the MONOTONE statement of the SAS® MI procedure using a model with indicator variables representing treatment sequence, Period 1 baseline score and Period 2 baseline score to create 300 imputed datasets.

Second, for each of the 300 imputed datasets and separately for each treatment period, intermittent missing score (missing period D1H3 score) will be imputed using a MCMC method in conjunction with the IMPUTE = MONOTONE option of the SAS® MI procedure to create 300 monotone datasets. The model will include in the following indicator variable representing treatment sequence, and continuous variables for Period i baseline, Period i D1H3, and Period i D21 where $i = 1, 2$.

Details regarding indicator variables are described in [Section 12.5.2.1.2](#).

12.5.2.1.6 Pattern Mixture Model Placebo-based Multiple Imputation Method

The Pattern mixture placebo-based multiple imputation method which is a “copy to reference method” will be implemented using baseline to predict D1H3 and D21 values in a MNAR model with indicator variables for treatment period, treatment sequence, and treatment.

For each of the 300 monotone by treatment period datasets generated as described in [Section 12.5.2.1.5](#), the remaining missing data will be imputed separately for each treatment period within each treatment arm using the REGRESSION method in conjunction with the MONOTONE statement and either MNAR or MAR statement (as described in [Table 12.5-1](#)) of the SAS® MI procedure.

- Step1, the imputation model will create 300 monotone by treatment period datasets, as described in [Section 12.5.2.1.5](#).
- Step 2a applied to Period 1 scores,
 - For patients on placebo treatment arm (i.e. placebo/nabiximols treatment sequence) and/or due to COVID-19 with non-missing LLMT-6 baseline score, LLMT-6 scores will be imputed sequentially at each post period baseline assessment (D1H3, D21) using a MAR imputation based on all non-missing LLMT-6 scores. Therefore, the models used to generate each post period baseline LLMT-6 scores are:
 - placebo LLMT-6 Period 1 D1H3 = placebo LLMT-6 Period 1 baseline score.
 - placebo LLMT-6 Period 1 D21 = placebo LLMT-6 Period 1 baseline score and placebo Period 1 D1H3 LLMT-6 score.
 - For patients on nabiximols treatment arm (i.e. nabiximols/placebo treatment sequence) with non-missing LLMT-6 baseline score, LLMT-6 scores will be imputed sequentially at each post period baseline assessment (D1H3, D21) using a MNAR imputation based on all non-missing LLMT-6 scores. Therefore, the models used to generate each post period baseline LLMT-6 scores are:

- nabiximols LLMT-6 Period 1 D1H3 = placebo LLMT-6 Period 1 baseline score.
- nabiximols LLMT-6 Period 1 D21 = placebo LLMT-6 Period 1 baseline score and placebo Period 1 D1H3 LLMT-6 score.
- Step 2b applied to Period 2 scores,
 - For patients on nabiximols treatment arm (i.e. placebo/nabiximols treatment sequence) and/or due to COVID-19 with non-missing LLMT-6 baseline score, LLMT-6 scores will be imputed sequentially at each post period baseline assessment (D1H3, D21) using a MAR imputation based on all non-missing LLMT-6 scores. Therefore, the models used to generate each post period baseline LLMT-6 scores are:
 - For patients on placebo treatment arm (i.e. nabiximols/placebo treatment sequence) with non-missing LLMT-6 baseline score, LLMT-6 scores will be imputed sequentially at each post period baseline assessment (D1H3, D21) based on all non-missing LLMT-6 scores.
 - If data is missing due to Period 1 withdrawal the procedure will use a MAR imputation and the models used to generate each post period baseline LLMT-6 scores are:
 - placebo LLMT-6 Period 1 D1H3 = placebo LLMT-6 Period 1 baseline score.
 - placebo LLMT-6 Period 1 D21 = placebo LLMT-6 Period 1 baseline score and placebo Period 1 D1H3 LLMT-6 score.
 - If data is missing due to not due to Period 1 withdrawal the procedure will use a MNAR imputation and the models used to generate each post period baseline LLMT-6 scores are:
 - placebo LLMT-6 Period 1 D1H3 = placebo LLMT-6 Period 1 baseline score.
 - placebo LLMT-6 Period 1 D21 = placebo LLMT-6 Period 1 baseline score and placebo Period 1 D1H3 LLMT-6 score.
- Step 3, Each of the 300 LLMT-6 scores generated from the fit of 300 placebo-based imputation models for each missing LLMT-6 score generated in Step 2 will correspond to a unique imputation number, and combination of imputed and non-missing LLMT-6 scores for each result in 300 complete datasets.
- Step 4: Imputed values from each of the 300 imputation datasets selected from step 3 and non-missing LLMT-6 scores will be analyzed by a linear mixed-effects model for crossover data applied to D21 as described in [Section 12.5.2.1.8](#).
- Step 5: Result from each linear mixed-effects model for crossover data will be combined as described in [Section 12.5.2.1.7](#).

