
The primary estimand for this study is defined by the following 4 components:
 
 • Population: Patients with MS, naïve to treatment with nabiximols who have not achieved adequate relief from spasticity with other antispasticity agents but have optimized treatment with at least 1 oral antispasticity drug. • Treatment: • Endpoint: Change in LLMT-6 from Day 1 pre-dose to D21 and from Day 31 pre-dose to Day 51. • Intercurrent events: 
 ○ Treatment-policy: Intercurrent events of non-adherence with IMP, use of prohibited medications, or other protocol deviations will be handled following a 'treatment-policy' strategy. Study data will continue to be collected and analyzed following the occurrence of the intercurrent event, i.e., the measure of effect is regardless of non-compliance, use of prohibited medications, or other protocol deviations. For patients who discontinue IMP, only the period in which this intercurrent event occurs will follow a treatment-policy strategy. Data will continue to be collected and analyzed following the occurrence of the intercurrent event up to the end of the period. ○ Hypothetical strategy: For patients who discontinue IMP during Period 1, their Period 2 data will be assumed to follow a hypothetical strategy, i.e., patients will be assumed to follow a similar pattern of data in Period 2 to those patients in the same Period 2 treatment arm who did not experience this intercurrent event during Period 1. For these patients, Period 2 data will not be collected, and these data will be imputed according to Table 9.1-3. 
Summary Measure: Mean difference in 'change from period level baseline to 21 days of the period assigned to nabiximols' compared to 'change from period level baseline to 21 days of the period assigned to placebo' regardless of treatment compliance and change of other antispasticity medications; following a treatment policy and hypothetical strategy for handling intercurrent events (as described above).

Secondary Estimand

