12.5.2.1.1 Missing Data Handling

As stated in [Section 9.1](#), under the hypothetical strategy for handling intercurrent events, Period 2 data will not be collected when patients discontinue IMP during Period 1. In addition, missing data within a single period only may arise if patients decide to withdraw from the study or are lost to follow-up.

For patients who discontinue study before entering Period 2,

- Not collected Period 1 data will be imputed under the missing at random (MAR) assumption if the patient withdraws from the study due to a reason relative to COVID-19 or if the patient is randomized to the placebo/nabiximols treatment sequence and will be imputed under the control-based missing not at random (MNAR) assumption otherwise (i.e., patient lost to follow up or prematurely withdraws from the study and randomized to nabiximols/placebo treatment sequence),
- Not collected Period 2 data will be imputed under the MAR assumption whether or not missing data arise under the hypothetical strategy and whatever the treatment sequence the patient is randomized to.

For patients who discontinue study but enter in Period 2 not collected Period 2 data will be imputed,

- under the MAR assumption if the patient withdraws from study due to a reason relative to COVID-19 and/or is randomized to the placebo/nabiximols treatment sequence,
- under the control-based MNAR assumption otherwise.

Under this framework, for those patients having their missing scores assumed MNAR, their mean profile will be assumed to be the same as those patients in the placebo treatment arm for the period containing the missing data. Details regarding missing data handling are given in [Table 12.5-1](#) below.

Table 12.5-1 Scenarios for Methods of Imputation when Data are not Collected

Scenario	Missing Data	Period 1 Imputation	Period 2 Imputation
1. Data not collected under the hypothetical strategy for handling intercurrent events	Period 2 data not collected due to patients who discontinue IMP or withdraw during Period 1/washout	N/A	Within treatment arm under MAR
2. Missing data arising due to reasons related to COVID-19, (and/or for patients assigned to placebo/nabiximols treatment sequence assignment)	Period 1 post baseline missing data but patient continues in study at least up to Period 2 baseline	Within treatment arm under MAR	Within treatment arm under MAR
	Period 1 withdrawal	Within treatment arm under MAR	Within treatment arm under MAR (Scenario 1)

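### Period 2 scores are imputed without the patient's own observed Period 1 D1H3 and D21, and both Step 2b placebo branches print Period 1 equations

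*SAP*

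**What the plan says.** Patients who stop IMP in Period 1 are followed to the end of that period, and Period 2 is then not collected. SAP Table 9.1-2 says of the period in which they stop: "Data will continue to be collected and analyzed following the occurrence of the intercurrent event up to the end of the period". So a patient with no Period 2 data can have an observed Period 1 D21. For Period 2 the hypothetical strategy is that "patients will be assumed to follow a similar pattern of data in Period 2 to those patients in the same Period 2 treatment arm"; the comparison patients are those free of the event in Period 1.

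SAP 12.5.2.1.1 makes this a missing-at-random imputation in both sequences: "Not collected Period 2 data will be imputed under the MAR assumption whether or not missing data arise under the hypothetical strategy". Scenario 1 of Table 12.5-1 covers "Period 2 data not collected due to patients who discontinue IMP or withdraw during Period 1/washout".

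The models are these:

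- **Period 2 baseline** (12.5.2.1.5): a regression with "indicator variables representing treatment sequence, Period 1 baseline score and Period 2 baseline score".
- **Period 2 D1H3 and D21** (12.5.2.1.6): "the remaining missing data will be imputed separately for each treatment period within each treatment arm using the REGRESSION method". Every printed equation uses the baseline and D1H3 of one period only.
- **Step 2b, Period 2, placebo arm**: the lead sentence says "LLMT-6 scores will be imputed sequentially at each post period baseline assessment (D1H3, D21) based on all non-missing LLMT-6 scores". The D21 equation printed in both the MAR and the MNAR branch is "placebo LLMT-6 Period 1 D21 = placebo LLMT-6 Period 1 baseline score and placebo Period 1 D1H3 LLMT-6 score", the same as in Step 2a.

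The Period 2 nabiximols equations are not visible in the text supplied; the same form is assumed here.

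**The concern.** There are two separate problems.

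1. **Omitted predictors.** If Period 1 and Period 2 changes are correlated, the patient's Period 1 scores are informative about the missing Period 2 scores. The analysis model in 12.5.2.1.8 uses that covariance (unstructured across periods), but no printed imputation model does. Precision is lost. If loss before Period 2 depends on Period 1 response, a missing-at-random assumption that does not condition on that response also moves the estimate whenever the loss is uneven between sequences.
2. **Wrong equations.** Read literally, Step 2b fills Period 2 placebo scores in the nabiximols/placebo sequence from Period 1 placebo patients in the other sequence. That contradicts Table 9.1-2 and ignores any period effect. It is probably a copy error, but it stands in the primary analysis.

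The tipping-point analysis (12.5.2.2) cannot show the first problem. Period 2 scores of patients lost before Period 2 are imputed under MAR in both sequences and receive no delta.

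**Working it through.** **Plan's own figures.** SAP 8.2 gives a paired SD of 0.71, a difference of -0.30 and two-sided 5%. A noncentral-t calculation with 46 completers gives 80.1% power, and 46/0.9 = 51.1, so 52 randomised. With 68 completers and SD 0.71, power is 93.0%, in line with the SAP. These figures are not in dispute.

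**Assumptions.** 76 randomised (68/0.9 = 75.6), 38 per sequence. The correlation of changes between periods, rho, is not in the documents, so 0.3, 0.5 and 0.7 are shown. The SD of change that keeps the paired SD at 0.71 is 0.71/√(2(1-rho)) = 0.60, 0.71 and 0.92; 0.7 is an upper case. The complete-data SE is 0.71/√76 = 0.081.

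**Closed form.** Suppose a share p of one sequence leaves, with mean Period 1 change d above the sequence mean (less improvement). Those who stay are then p·d/(1-p) below it in Period 1 and rho times that in Period 2, and the imputation copies their Period 2 level. The treatment estimate is half the between-sequence contrast, so its shift is rho·p·d/(2(1-p)). With d = 1 SD and p = 10%:

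- rho 0.5: 0.5 × 0.10 × 0.71/1.8 = 0.020
- rho 0.7: 0.7 × 0.10 × 0.92/1.8 = 0.036

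The shift favours nabiximols if the loss is in placebo/nabiximols, and goes against it if the loss is in nabiximols/placebo.

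**Simulation.** 1280 trials per scenario, 25 imputations, mixed model with unstructured covariance, Rubin's rules. Baseline SD 0.8 with between-period correlation 0.8; changes independent of baseline; D1H3 change with 0.6 times the SD of the D21 change and correlation 0.4 with it. Response-dependent loss has a logit slope of 1.5 per SD of Period 1 change. Shift means the difference from the estimate with no missing data (Monte Carlo SE 0.0006 to 0.0012).

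*Random loss, 10% of Period 2:*

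| rho | SE, SAP | SE, Period 1 scores added | Power, SAP | Power, added |
|---|---|---|---|---|
| 0.3 | 0.087 | 0.086 | 0.94 | 0.94 |
| 0.5 | 0.091 | 0.087 | 0.92 | 0.93 |
| 0.7 | 0.099 | 0.088 | 0.87 | 0.92 |

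Coverage under the SAP rule is 96 to 98%.

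*Poor responders lost, 15% v 5%, Period 1 D21 on IMP; shift under the SAP rule:*

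| More loss in | Dependence in | rho 0.3 | rho 0.5 | rho 0.7 |
|---|---|---|---|---|
| nabiximols first | both sequences | +0.009 | +0.019 | +0.034 |
| nabiximols first | one sequence | +0.015 | +0.031 | +0.055 |
| placebo first | both sequences | not shown | -0.020 | -0.036 |
| placebo first | one sequence | not shown | -0.031 | not shown |

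Milder cases at rho 0.5, dependence in both: half the slope +0.012; 12% v 8% +0.008; 10% v 10% +0.001. With Period 1 scores added, the shift is within 0.001 throughout.

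*Period 1 D21 of nabiximols stoppers recorded off IMP.* The effect is assumed fully lost (+0.30) and the loss is 15% v 5%. Using that D21 should move the estimate by about -0.5 × rho × 0.15 × 0.30 = -0.011 at 0.5 and -0.016 at 0.7. Simulated:

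| rho | Loss | SAP | All Period 1 scores | Baseline and D1H3 only |
|---|---|---|---|---|
| 0.5 | random | 0.000 | -0.012 | 0.000 |
| 0.5 | dependent, both | +0.019 | -0.013 | +0.016 |
| 0.5 | dependent, one | +0.032 | -0.011 | +0.027 |
| 0.7 | random | -0.001 | -0.017 | not shown |
| 0.7 | dependent, both | +0.035 | -0.017 | not shown |

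**Period 1 equations read literally.** With 10% loss and an assumed period effect of 0.20, the shift is 0.5 × 0.10 × 0.20 = +0.010, confirmed by simulation.

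**Would the planned analyses show it?** The completer analysis (12.5.4.3.2) errs in the opposite direction. At rho 0.5 in the response-dependent case, its estimate minus the SAP estimate averages -0.039 (both) or -0.062 (one), against an SD of 0.027 under random loss. It passes twice that SD in about 35% and 59% of trials. With random loss and an off-IMP D21 the gap is -0.022 although the SAP rule has no shift, so the gap is a signal but not a correction.

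**Second simulation.** Separately coded, with 1000 trials per scenario, it agrees in direction and size. With 20% response-dependent loss in one sequence and 52 patients, shifts are 0.024 to 0.093 in size under the SAP rule and at most 0.005 with Period 1 scores added.

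**The case against.** **The labels are resolved elsewhere.** 12.5.2.1.1 says that control-based imputation follows placebo patients in the period with the missing data, and Table 9.1-2 points to the same Period 2 arm. So the intent is clear, but the printed equations still contradict it and need correcting.

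**The estimand may not condition on Period 1.** Assuming that stoppers look like same-arm patients without the event fits imputation by period and arm; on that reading the shift is not bias. This stands in part. Table 9.1-2 does not settle it, while the Period 2 baseline model already conditions on Period 1 baseline and Step 2b claims to use all available scores.

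**Off-IMP D21.** For patients who stop IMP, Period 1 D21 is generally an off-treatment score. Using it can then move the estimate towards nabiximols where the SAP rule has no shift. This stands, and it is why a second run is needed.

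**Size.** The 15% v 5% case is about 6 v 2 patients of 38, and +0.019 is about 0.2 SE. Balanced loss cancels, and at rho 0.3 there is little or nothing to gain. In the second simulation, with 20% random loss and 52 patients, the SE was 0.118 under the SAP rule and 0.119 with the added scores. With 20% response-dependent loss in both sequences and 76 patients, the spread of estimates was larger with them (0.0976 v 0.0939). The gain therefore depends on a moderate correlation. The 0 to 5 truncation of imputed scores is not part of the simulation as described.

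**Conclusion.** The concern holds. Step 2b is wrong as written for Period 2 placebo scores. No printed Period 2 model uses the patient's observed Period 1 D1H3 or D21.

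The consequences are conditional and modest. At 10% random loss the primary SE is about 1%, 4 to 5% or 13% larger than necessary at rho 0.3, 0.5 or 0.7, without harm to coverage. With uneven, response-dependent loss of 15% v 5%, the shift is about 0.01 to 0.055 in size, in either direction, against a target of 0.30; with equal loss and dependence it is about zero. Correlation, loss pattern and strength of dependence are all assumptions, so confidence in the size is medium. Neither rule is free of shift when Period 1 D21 is off IMP: there the two err on opposite sides.

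**What to change.** Before database lock and unblinding:

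1. Rewrite both Step 2b placebo branches with Period 2 variables.
2. Impute in time order, with Period 1 baseline, D1H3 and D21 where observed:
   - Period 2 baseline = sequence + Period 1 scores
   - Period 2 D1H3 = Period 2 baseline + Period 1 scores
   - Period 2 D21 = Period 2 baseline + Period 2 D1H3 + Period 1 scores

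   Where Period 1 D21 is missing, use baseline and D1H3.
3. Pre-specify a second run that uses only Period 1 baseline and D1H3 for patients who stopped IMP in Period 1.
4. Report the treatment estimate of the observed-case mixed model already fitted in 12.5.2.1.9.
5. State in Table 9.1-2 whether the hypothetical Period 2 outcome is conditional on observed Period 1 scores. If it is not, remove the statement in 12.5.2.1.6 that the imputation draws on all available scores.
6. Apply the same changes to LLMT-4 and LLMT-10.

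**Cost.** Up to three more covariates in the imputation regressions, corrected text and one extra run; no new data. The models are fitted to about 30 to 38 patients per arm, and the SE is about 1% larger if the correlation is 0. If half of the losses lack Period 1 D21, the SE gain at rho 0.5 falls from 5% to 3%. The second run removes the off-IMP shift but keeps most of the response-dependent one. The observed-case model is within 0.001 in the on-IMP cases but has the same off-IMP shift (-0.012 at rho 0.5). The runs therefore have to be read together.

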12.5.2.1.7 Combining multiple imputation results

The analysis models will be evaluated in each imputed dataset and, the point estimates and SEs will be combined using Rubin's rules to produce valid global estimates with corresponding CIs and p-values. SAS® MIANALYSE procedure will be used for this purpose (Rubin, 1976).

12.5.2.1.8 Linear Mixed-effects Model for Crossover Data

The primary analysis model will be selected before multiple imputation and all subsequent statistical analysis conducted on this final model. The final selected model (after convergency and residual diagnostics and outlier searches, see below) will be fitted to each of the 300 imputed datasets. The model selection process will NOT be reconducted for each imputed dataset.

The change from baseline to D21 of each treatment period (as defined in [Section 10.2](#) and [Section 10.3](#)) in LLMT-6 (as defined in [Section 10.16](#)) will be analyzed with a LME model for crossover data using the SAS® GLIMMIX procedure with an identity link function and a normal distribution. The change from period level baseline to D21 in LLMT-6 score will be included as the dependent variable. Hence, each patient will contribute two measurements to the model, one for each period of the study.

The preferred model will include a period level LLMT-6 baseline (pre-dose measurement) covariate, period level treatment arm, treatment period, and treatment sequence as fixed effects). An unstructured (UN) covariance structure will be used for the repeated LLMT-6 measurements of the changes from baseline in each treatment period and the denominator degrees of freedom will be calculated according to the Kenward-Roger method (e.g., KR2, 2009 version)

In case of non-convergence of the preferred model or memory space issue, the compound symmetry covariance structure will be applied to the preferred model described above.

This model will provide the least squares mean estimates for each treatment arm, along with the SEs and 95% CIs as well as, the least squares mean (LS mean) estimate of the mean treatment difference between nabiximols and placebo in change from baseline in LLMT-6 along with SE of the difference, 95% CI and associated nominal p-values will be presented.

In addition, this model will present the LSmeans estimates along with 95% CIs for each treatment period and treatment sequence, as well as the difference between treatment periods and treatment sequences and associated nominal p-values.

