13.6.2 Primary Endpoint

The primary endpoint is the change in LLMT-6 from Day 1 predose to Day 21 and from Day 31 predose to Day 51. The MAS scores are transformed using the following algorithm: MAS untransformed [to MAS transformed] scores; 0[0], 1[1], 1+[2], 2[3], 3[4], and 4[5].

The primary estimand is the mean treatment difference (nabiximols – placebo) in the mean change from baseline in LLMT-6 from Day 1 (predose) to Day 21 and from Day 31 (predose) to Day 51 for all randomized patients.

For any given patient, at a given visit, the LLMT-6 will be set to missing if individual MAS transformed scores are missing for 3 or more of the 6 specified muscle groups.

The change from baseline in LLMT-6 will be analyzed using a linear mixed-effects model for crossover data. The model will include a period level LLMT-6 baseline covariate, and treatment, period, and treatment sequence as fixed effects, and patient nested within treatment sequence as a random effect. Mean change from baseline in LLMT-6 will also be summarized by treatment sequence, over time.

The least squares mean estimates for each treatment, along with the standard error and 95% confidence intervals (CIs), will be presented. In addition, estimate of the mean treatment difference in change from baseline in LLMT-6 will be presented along with standard errors of the difference and 95% CIs.

If the data appear to not be normally distributed, alternative approaches such as transformation of the data and nonparametric analyses may be considered to express treatment effects. This will be specified in detail in the SAP.

Further details of statistical analyses will be elaborated in the SAP.

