8.2 Sample Size Considerations

Approximately 26 patients will be randomly assigned to each treatment sequence to ensure that at least 46 patients in total complete the 2 treatment periods. The primary comparison will be the estimate of the mean treatment difference between nabiximols and placebo in the mean change from baseline in LLMT-6.

Assuming a standard deviation of the paired differences between nabiximols and placebo of 0.71 and a treatment difference of -0.30, 46 patients will provide 80% power using a 5% significance level and a two-sided test. Adjusting for 10% dropout, a total of approximately N=52 patients are required. If more than 6 patients withdraw from the trial, additional patients will be enrolled to have 46 completers.

A blinded sample size re-estimation was conducted based on methodology in section 11.1 and the estimated standard deviation of the pooled treatment period differences (treatment period 2 – treatment period 1) in changes from baseline to D21 in MAS was larger than 0.71 (the assumed standard deviation of the treatment differences at design stage). Using this new standard deviation as the estimate of the standard deviation of the treatment differences (nabiximols – placebo) of the changes from baseline to D21 in MAS, the sample size was recalculated. In a blinded sample size re-estimation committee meeting dated 30th November 2021, the committee recommended increasing the sample size to 68 completers. This new sample size will result in at least 80% power for this study if the new observed blinded standard deviation were the true unblinded standard deviation, and greater than 90% power if the true unblinded standard deviation was exactly 0.71.

SAS software version 9.4 was used to perform the sample size calculations.

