9.2 Predetermined Covariates and Prognostic Factors and other Analyzed Factors

The following factors will be adjusted for as covariates and used in the analysis models as fixed effect:

- Treatment sequence, which has two levels: nabiximols/placebo (coded as 1) and placebo/nabiximols (coded as 2),
- Treatment period, which has two levels: Period 1 (coded as 1) and Period 2 (coded as 2),
- Baseline / Period baseline (as continuous covariates)

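### The primary LLMT-6 model fits one slope to a baseline that varies within patient, which can leave precision unused; adding the patient-mean baseline is a cheap improvement

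*SAP*

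**What the plan says.** The outcome in the primary model is a change score (SAP 12.5.2.1.8): "The change from period level baseline to D21 in LLMT-6 score will be included as the dependent variable". The baseline term is set out as: "The preferred model will include a period level LLMT-6 baseline (pre-dose measurement) covariate", alongside treatment arm, period and sequence as fixed effects. The two records of a patient are linked through the residual covariance: "An unstructured (UN) covariance structure will be used for the repeated LLMT-6 measurements of the changes from baseline in each treatment period", with compound symmetry as the fallback.

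Protocol 13.6.2 gives the same fixed part, "The model will include a period level LLMT-6 baseline covariate, and treatment, period, and treatment sequence as fixed effects", with patient as a random effect nested in sequence.

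SAP 9.2 lists "Baseline / Period baseline (as continuous covariates" among the covariates without saying whether one term or two is meant. SAP 12.5.2.1.8 names only the period-level term. Neither document mentions the patient's mean baseline, the baseline difference between periods, or separate within- and between-patient slopes. LLMT-4 (SAP 12.5.3.1) and LLMT-10 (SAP 12.5.4.1) follow the primary model.

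**The concern.** Each patient has two predose baselines, Day 1 and Day 31. A single coefficient on the period-level value describes two different relations: how change relates to baseline across patients, and how the difference in change relates to the difference in baseline within a patient. Only the second bears on the treatment difference, whose variance is smallest at the within-patient slope.

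Because patients are not fixed effects, between-patient information also feeds the single coefficient. The more patients differ from one another, the closer that coefficient moves to the between-patient slope, and the more period-specific baseline noise stays in the treatment contrast. At stake is the precision of the primary and key secondary estimates, using data the trial already collects.

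**Working it through.** **Inputs from the documents.** SAP 8.2: "Assuming a standard deviation of the paired differences between nabiximols and placebo of 0.71 and a treatment difference of -0.30", and "46 patients will provide 80% power using a 5% significance level and a two-sided test". Dropout is 10%, giving 52 patients. The size after blinded re-estimation is 68 completers.

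**Reproducing the plan's figures.** A paired t test (noncentral t) with difference 0.30 and SD 0.71 has 80.1% power at 46. For dropout, 46/0.9 = 51.1, and 52 is the next even number. At 68 completers and SD 0.71 the power is 93.0%, in line with the SAP's statement of more than 90%. These calculations contain no baseline covariate.

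**Assumptions, because the documents do not give them.** Baseline = patient effect + b, and D21 score = patient effect + e. The variances of b and e are equal (s²), their correlation within a period is ρ, and there is no carry-over into the Day 31 baseline. The between-patient SD σ is taken as 0.3 to 0.8 and ρ as 0 to 0.9.

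**Formulas on the change scale.**
- Fixing the unadjusted SD at 0.71: 4s²(1-ρ) = 0.71² = 0.5041, so s² = 0.126/(1-ρ).
- Within-patient slope: w = -(1-ρ).
- Between-patient slope: -(1-ρ)(s²/2)/(σ² + s²/2).
- Common slope c: the value that minimises log var(sum residual) + log var(difference residual), which is the likelihood criterion for a free 2×2 covariance with equal period variances.
- Variance of the within-patient difference with separate slopes: 0.5041(1+ρ)/2.
- The same with one slope: that value plus 2s²(c-w)².

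**Example, σ = 0.8 and ρ = 0.5.** s² = 0.252, w = -0.50, between-patient slope = -0.063/0.766 = -0.08, and c = -0.15. Separate slopes give 0.5041 × 0.75 = 0.378 (SD 0.615). One slope gives 0.378 + 0.504 × 0.35² = 0.440 (SD 0.66). The ratio is 0.86.

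| σ | ρ | within | between | common | SD, one slope | SD, separate | variance ratio, separate/one |
|---|---|---|---|---|---|---|---|
| 0.3 | 0 | -1.00 | -0.41 | -0.64 | 0.534 | 0.502 | 0.88 |
| 0.5 | 0 | -1.00 | -0.20 | -0.38 | 0.591 | 0.502 | 0.72 |
| 0.8 | 0 | -1.00 | -0.09 | -0.18 | 0.650 | 0.502 | 0.60 |
| 0.3 | 0.5 | -0.50 | -0.29 | -0.37 | 0.621 | 0.615 | 0.98 |
| 0.5 | 0.5 | -0.50 | -0.17 | -0.26 | 0.638 | 0.615 | 0.93 |
| 0.8 | 0.5 | -0.50 | -0.08 | -0.15 | 0.664 | 0.615 | 0.86 |

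These are large-sample values, so they omit the cost of estimating the extra term.

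**Simulation at 68 completers** (unstructured covariance). For σ = 0.5 and 0.8, the variance ratios were 0.75 and 0.60 at ρ = 0, 0.95 and 0.87 at ρ = 0.5, 1.00 and 0.97 at ρ = 0.75, and 1.01 and 0.99 at ρ = 0.9. Another run over σ from 0.3 to 0.8 gave 0.65 to 1.01. The favourable corner is therefore a reduction of about 35% to 40%, and the unfavourable one an increase of about 1%.

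**Simulation at 46 completers** (800 runs per scenario, t reference in place of Kenward-Roger):

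| σ, ρ | | no baseline | one slope | slope + patient mean |
|---|---|---|---|---|
| 0.8, 0 | SE | 0.102 | 0.093 | 0.075 |
| | power | 84% | 90% | 98% |
| 0.8, 0.5 | SE | 0.106 | 0.099 | 0.092 |
| | power | 78% | 83% | 89% |

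Mean estimates ran from -0.296 to -0.309 against a true -0.30. Type I error was about 4% to 6% for all three models, and model SEs matched empirical SEs. For σ 0.3 to 1.1 and ρ 0 to 0.7, the large-sample variance with one slope was 0.57 to 0.93 of the variance with no baseline term.

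**The case against.** The strongest case against is that nothing here is an error. The single-slope model is pre-specified, agrees between protocol and SAP, is unbiased, holds its type I error and beats no adjustment. The gain depends on two quantities the documents do not report, and the large figures need a correlation near zero. If 0.71 were the true SD, an unadjusted test would already have 93% power at 68 completers. All of that stands, and it makes this an efficiency point only.

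The fix also reaches further than one line:
- SAP 12.5.2.1.5 imputes a missing Period 2 baseline only when the Period 1 baseline is present.
- SAP 12.5.2.1.6 imputes each period from that period's own scores.
- The subgroup, repeated-measures and T25FW models reuse or extend the primary one.

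These objections call for a more careful fix, but they do not remove the gain.

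Three stronger readings are tempting, and the documents support none of them:
- A reader might infer that the variance is inflated outright. It is larger only than with separate slopes.
- A reader might think the between-patient slope is the steeper one. That is so if the D21 score is the outcome (each slope plus 1), but the SAP models change, where it is flatter.
- A reader might take the rise from 46 to 68 completers as evidence of the problem. SAP 8.2 and 11.1 base that step on unadjusted period differences in change, so the slope played no part in it.

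**Conclusion.** The point holds as a possible loss of precision, not as a flaw in validity. The single slope is a compromise between the two relations, closer to the between-patient value when patients differ widely.

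Over the assumed ranges, adding the patient-mean baseline moves the variance of the treatment difference by between about -35% to -40% and +1%. The gain fades as baseline deviations persist to D21: at ρ = 0.75 or more it was 0% to 3% in the simulations at 68 completers. It is also smaller when patients differ little: at σ = 0.3 it is 12% at ρ = 0 and 2% at ρ = 0.5 in large samples.

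The conclusion rests on the assumed variance components, equal variances at baseline and D21, complete data and no carry-over. The case for the change is the asymmetry: a possibly useful gain against a loss of about 1%.

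**What to change.** Before unblinding:
- Keep the period-level baseline and add the patient's mean of the two period baselines as a second covariate in the LLMT-6, LLMT-4 and LLMT-10 models. Carry it into the subgroup models (SAP 12.5.2.3.1) and the repeated-measures models (SAP 12.5.4.2).
- State that a patient with one unavailable period baseline is kept, with the available baseline used as the mean.
- Put both period baselines into the imputation models of SAP 12.5.2.1.5 and 12.5.2.1.6, so that they contain every predictor in the analysis model.
- Say whether the T25FW model (SAP 12.5.5.1), which borrows the primary model, follows the change.
- Make the covariate list in SAP 9.2 name both terms, and record the departure from Protocol 13.6.2 in SAP 6.2.

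The cost is one between-patient degree of freedom, about 1% of variance at worst in the scenarios run, and small edits to the imputation and dependent models. If the sponsor prefers to keep the primary model, the two-covariate version can be pre-specified as a supplementary analysis.
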